Participants will continue to provide blood samples for PK assessments, for 8 hours, posttreatment (see PK Sampling in the SoE, Table 2) and complete any protocol-mandated QoL/PRO assessments. After the 8-hour PK sample is collected (unless there was reason to prematurely discontinue participation sooner), participants will be evaluated to determine if they can be discharged to home (accompanied by a trusted adult) or if they need to be monitored for an extended period and/or if additional medical intervention will be needed. Participants will leave with and continue to wear the health tracking device.

Study Day 2: Participants will return to the study site the next day, as close to 24 hours after the time of study drug administration on Study Day 1. Participants will have vital signs measured, share any changes in concomitant medications and complete an in-person group and an individual integration session. Participants also will be assessed for adverse events and be administered clinician rating scales for suicidal ideation/behavior, depression, and anxiety in addition to completing QOL and PRO instruments (see SOE).

Study Day 4: Approximately 72 hours after the time of study drug administration on Study Day 1, participants will undergo an individual virtual (via web meeting, phone, etc.) integration session and assessed for adverse events including mental health issues as well as for changes in concomitant medications.

Study Day 8: One week following Study Day 1, participants will return to the study site to undergo a physical exam, have vital signs measured, share any changes in concomitant medications and be assessed for adverse events. Participants also will be administered clinical rating scales and complete their QoL and PRO instruments. Participants also will provide blood and saliva samples for clinical laboratory evaluations and for epigenetic testing.

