1. LIST OF ABBREVIATIONS

Item	Description
5D-ASC	5-Dimensional Altered States of Consciousness Rating Scale
AE(s)	Adverse events
ALP	Alkaline phosphatase
ALT / SGPT	Alanine aminotransferase / Serum glutamic pyruvic transaminase
AST / SGOT	Aspartate aminotransferase / Serum glutamic-oxaloacetic transaminase
AUC _{0-t}	Area under the concentration-time curve (AUC) from time zero (i.e., dosing time) to the time of the last quantifiable concentration.
AUC _{0-∞}	The AUC from time zero extrapolated to infinity using linear regression.
AUDIT	Alcohol Use Disorders Identification Test
BP	Blood pressure
BPI	Brief Pain Inventory
bpm	Beats per minute
BUN	Blood urea nitrogen
°C	Centigrade (temperature)
CBF	Cerebral blood flow
CEQ	Challenging Experience Questionnaire
C _{max}	Maximum observed concentration
C-SSRS	Columbia Suicide Severity Rating Scale
DEA	Drug Enforcement Administration
DMN	Default mode network
DMT	N,N-Dimethyltryptamine
DSM-5	Diagnostic and Statistical Manual of Mental Disorders – 5 th edition
DSMB	Data Safety Monitoring Board
DUDIT	Drug Use Disorders Identification Test
eCRF	Electronic case report form
ECG	Electrocardiogram
EDC	Electronic data capture
EoT	End of Treatment (visit)
°F	Fahrenheit (temperature)
FDA	Food and Drug Administration
fMRI	Functional magnetic resonance imaging
GCP	Good Clinical Practice
GAD-7	Generalized Anxiety Disorder 7-Item Scale
GGT	Gamma-glutamyl transferase
hCG	Human chorionic gonadotropin

CONFIDENTIAL

HIPAA	Health Insurance Portability and Accountability Act
HR	Heart rate
HRV	Heart rate variability
ICF	Informed Consent Form
IRB	Institutional Review Board
IUD	Intrauterine device
LDH	Lactate Dehydrogenase
LEC-5	Life Events Checklist for DSM-5
LSD	Lysergic acid diethylamide
LTFU	Long-term follow-up visit (~90 days / 3 months)
m ²	Meter squared
MAO	Monoamine oxidase inhibitors
MCH	Mean corpuscular hemoglobin
MCV	Mean corpuscular volume
MEQ30	Mystical Experience Questionnaire – Revised
mg	Milligram
min(s)	Minute(s)
mL	Milliliter
NCI CTCAE	National Cancer Institute's Common Terminology Criteria for Adverse Events
NIH HEALS	Healing Experience of All Life Stressors
PCL-5	PTSD Checklist for DSM-5
pH	Concentration of hydrogen
PHQ-9	Patient Health Questionnaire-9
pK	Pharmacokinetic
POMS	Profile of Mood States
PRN	Pro re nata (as needed)
PRO	Patient reported outcome
PTSD	Post-traumatic stress disorder
QoL	Quality-of-Life
QT (interval)	ECG measured: Q-wave to T-wave time duration
RBC	Red blood cell
RR	Respiration rate

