SAE(s)	Serious Adverse Events
SDS	Sheehan Disability Scale
SoE	Schedule of Events
SpO ₂	Peripheral capillary oxygen saturation
SSRI	Selective serotonin reuptake inhibitor
TBI	Traumatic brain injury
TEAE	Treatment emergent adverse event

CONFIDENTIAL

T _{max}	Time to reach maximum observed concentration during a dosing interval
t _{1/2}	Time to reach one-half of the original, maximum observed concentration
UGT	UDP-glucuronosyltransferase
ULN	Upper limit of normal range
WBC	White blood cell
WCS	Watts Connectedness Scale

2.BACKGROUND AND STUDY RATIONALE

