2.3.2 Psilocybin as a Potential Treatment for patients with PTSD

Psilocybin (4-phosphoryloxy-N, N-dimethyltryptamine) is a substituted indolylalkylamine and belongs to the group of hallucinogenic tryptamines. Psilocybin was first isolated in a mushroom species (*Psilocybe mexicana*) and also has been synthesized.

Pharmacokinetics

Psilocybin is a prodrug that is metabolized to psilocin. Psilocin, due to its lipophilicity, is able to cross the blood-brain barrier and produce neurological effects. After ingestion, psilocybin is rapidly converted to psilocin in the stomach, intestines, blood, and kidneys. Studies suggest fasting for 2-4 hours before taking psilocybin.

Psilocybin has about 50% bioavailability and is detectable in plasma within 20-40 minutes. Psilocin is detectable in plasma after 30 minutes and has linear pharmacokinetics. The half-life of psilocin is around 108 minutes, and its effects last 4-6 hours. Psilocin is mainly metabolized by the liver through UGT 1A10 and UGT 1A9 enzymes into psilocin-O-glucuronide and excreted through urine and feces, with complete excretion within 24 hours.

Pharmacodynamics and Psychedelic Effects

Psilocin, the primary active metabolite of psilocybin, is highly lipophilic and readily crosses the blood brain barrier. Psilocin has a high affinity for the 5-HT_{2A} serotonin receptor, which is responsible for its hallucinogenic effects, and that of many psychedelic drugs. Molecules that activate this receptor are known to stimulate the production of the brain-derived neurotrophic factor (BDNF) and enhance the efficiency of signaling between neurons.

The acute effects of psilocybin on brain activity have been graphically demonstrated in 2 functional magnetic resonance imaging studies, which showed how networks of regions that usually operate independently become more functionally interconnected, while connectivity within the ‘default mode network’—a network associated with mind-wandering and the sense of self—is disrupted (Carhart-Harris 2012; Carhart-Harris 2017). The default mode network is overactive in people who are prone to depression and is thought to be responsible for the excessive self-referential thought and rumination that characterizes depression. Therefore, alteration of this network, as shown by acute decreases in cerebral blood flow in key default mode brain regions, may guide the understanding of the antidepressant effects of psychedelics like psilocybin.

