One-to-One			X ¹⁵						
Group Session			X ¹⁵	X	X				
Ceremony				X					
GAD-7 ⁹		X		X	X	X	X	X	X
PHQ-9 ¹⁰		X		X	X	X	X	X	X
NIH-HEALS		X		X	X		X	X	X
BPI		X		X	X	X	X	X	X
C-SSRS ¹¹		X		X	X	X	X	X	X
POMS ¹²				X					
SDS		X						X	
WCS				X			X	X	
MEQ30-revised				X				X	
CEQ				X				X	
5D-ASC				X					
AUDIT ¹³		X						◆	X
DUDIT ¹³		X						◆	X
Adverse Events					X	X	X	X	X

CONFIDENTIAL

Footnotes:

1. Pre-Screen: Study site staff should obtain verbal consent to collect information to assess potential eligibility for the trial. If the individual does not qualify or chooses not to participate, the information collected will be deleted, save for more general, non-identifiable, information recorded on the Screening Log.
2. Height / Weight: Height and weight should be measured at Screening, but only weight will be measured at the Study Day 8 and EoT visits, respectively.
3. Physical Examination: The physical exam should be targeted to head, eyes, ears, nose, throat (HEENT), abdomen and extremities. A brief neurological exam also should be performed on cranial nerves 2 through 12 as well as assessments of motor reflexes and cerebellar function.
4. Vital Signs: Measure body temperature, pulse oximetry (SpO₂), heart rate, respiratory rate, and blood pressure
5. Urine Pregnancy: A urine sample should be collected for all females of childbearing potential. If needed, a serum-HCG test can be done to confirm an initial positive result.
6. Clinical Laboratory Tests: Blood samples will be collected to perform clinical laboratory evaluations. A urine sample, for urinalysis, only will be collected at Screening.
7. Electrocardiogram: A 12-lead ECG should be obtained. If there is a finding of QT interval prolongation (i.e., > 450 msec), then triplicate ECG recordings should be done within 5 (to 6) minutes for confirmation. If confirmed, the participant is not eligible to participate in the trial.
8. Pharmacokinetic: Blood samples for PK testing should be obtained at the following timepoints on Study Day 1: up to 30 minutes prior to study drug administration and then at the following timepoints after dosing — 30 minutes (±2 mins), 60 minutes (±5 mins), 90 minutes (±5 mins), 120 minutes (±5 mins), 4 hours (±15 mins) and 8 hours (±15 mins)
 - ^ To qualify for treatment, participants must self-report at least one traumatic event via the LEC-5 that the clinician considers causative for a diagnosis of PTSD; in addition, they must score at least 33 on the PCL-5

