9. GAD-7: If a participant's score is ≥15 at Screening or on Study Day 1 (prior to study drug administration), the participant is not eligible for treatment.
10. PHQ-9: If a participant's score is ≥20 at Screening or on Study Day 1 (prior to study drug administration), the participant is not eligible for treatment.
11. C-SSRS: If at Screening or on Study Day 1 a participant's 'suicidal' assessment is scored as Category 4 (i.e., Active Suicidal Ideation with Some Intent to Act, without Specific Plan) or Category 5 (Active Suicidal Ideation with Specific Plan and Intent), the participant is not eligible to continue to participate in the trial and should be referred for appropriate psychiatric care.
12. POMS: On Study Day 1, after all protocol-mandated activities are complete, the clinician will assess the result of the POMS. If the posttreatment POMS score is not ≤125% of the baseline, pre-dose, value, the patient should be held overnight for observation. [Otherwise, if the score is ≤125% of the baseline, and if there are no other problems, the patient may be discharged to home (accompanied by a trusted adult).
13. AUDIT / DUDIT: The AUDIT and DUDIT should be completed at the Study Day 30 / End-of-Treatment visit if a participant prematurely discontinues from the trial (for any reason) and will not undergo the 3-month, Long-Term Follow-up visit.
14. ◆: The diamond reflects tests, examinations, assessments or other procedures that are to be completed the EoT visit if a participant is prematurely discontinued from further involvement in the trial and the particular protocol-mandated activity was not performed at the Study Day 8 visit.
15. **The One-to-One session as well as the Group session require participants to return to the study site on separate days. [Thus, the Screening Period can require three (3) visits to the study site.]**

Table 2
Study Day 1 Schedule of Events

Activity	Pre-Dose	Dose		Post Dose							
		Time 0	30 mins	60 mins	90 mins	120 mins	150 mins	180 mins	240 mins 4 hours	4.5, 5.0, 5.5, 6.0, 6.5, 7.0 and 7.5 hours	480 mins 8 hours
Medical History	X										
Concomitant Medications	X										
Eligibility Criteria	X										
Height / Weight ²	X										
Vital Signs ⁴	X	X	X	X	X	X	X	X	X	X*	X
Urine Pregnancy Test ⁵	X										
Urine Drug / Alcohol Tests	X										
Clinical Laboratory Tests ⁶	X										
Electrocardiogram ⁷	X										
Saliva – Epigenetic Test	X										
Pharmacokinetic Test ⁸	X	X	X	X	X	X	X	X	X		X

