7.2. Pharmacokinetic Assessments

The pharmacokinetics (PK) of psilocin (the major active metabolite of psilocybin) will be investigated following self-administration of a single dose of a whole organic psilocybin mushroom.

The PK profile of psilocin will be assessed in plasma on Study Day 1. Blood samples will be processed and analyzed for concentrations of psilocin by a validated method. On Study Day 1, participants must self-administer the psilocybin mushroom in a fasted state and will remain fasted for a minimum of 4 hours following the administration of study drug.

The specific collection times for PK blood samples are outlined below.

Predose:

- Up to -30 minutes before study drug administration

Post Dose:

- 30 minutes / 0.5 hours (\pm 2 mins) post dose
- 60 minutes / 1.0 hour (\pm 5 mins) post dose
- 90 minutes / 1.5 hours (\pm 5 mins) post dose
- 120 minutes / 2 hours (\pm 5 mins) post dose
- 4 hours (\pm 15 mins) post dose

CONFIDENTIAL

- 8 hours (± 15 mins) post dose

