12.4. Analyses of Secondary Objectives

Non-compartmental analyses will be used to measure derived PK parameters for psilocin including AUC_{0-t} , $AUC_{0-\infty}$, T_{max} , C_{max} and $t_{1/2}$ (and perhaps others). The PK profile of psilocin will be listed and presented graphically. PK parameters of psilocin will be summarized descriptively.

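### The protocol gives two conflicting PK draw schedules, a 12-hour AUC that 8-hour sampling cannot deliver, and a definition of t1/2 that is not the terminal half-life

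*Protocol*

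**What the plan says.** **Draw times.** The Synopsis (Treatment Period, Study Day 1) states "Participants will continue to provide blood samples for PK assessments, for 8 hours, posttreatment" and sends the reader to the PK sampling in Table 2. Section 7.1 instead says that procedures follow Table 1. Table 1's footnote 8 begins "Blood samples for PK testing should be obtained at the following timepoints on Study Day 1" and lists pre-dose, 30, 60, 90 and 120 minutes, 4 h and 8 h. Sections 7.1.4 and 7.2 give the same post-dose times, and the list in 7.2 ends at "8 hours (± 15 mins) post dose". The Table 2 row headed "Pharmacokinetic Test" cites the same footnote 8. It carries marks at pre-dose, Time 0, 30, 60, 90, 120, 150, 180, 240 and 480 minutes and is blank only for 4.5 to 7.5 h.

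**AUC.** The Synopsis lists AUC0-12 and AUC0-∞ as secondary endpoints. Sections 4.4.2 and 12.4 list AUC0-t and AUC0-∞. The abbreviation list defines AUC0-t as "Area under the concentration-time curve (AUC) from time zero (i.e., dosing time) to the time of the last quantifiable concentration" and has no entry for a 12-hour AUC. Section 4.1 allows discharge after the 8-hour sample.

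**Half-life.** Section 12.4 says "Non-compartmental analyses will be used to measure derived PK parameters for psilocin", with t1/2 among them. The abbreviation list defines t1/2 as "Time to reach one-half of the original, maximum observed concentration". Section 2.3.2 gives the literature value: "The half-life of psilocin is around 108 minutes, and its effects last 4-6 hours".

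**The concern.** Staff who work from Table 2 would draw 10 samples, and staff who work from footnote 8 or the section text would draw 7. Each participant is dosed once, so a 150- or 180-minute sample that is not taken cannot be recovered, and no later analysis rule can replace it. If practice varied, the profiles would also not be comparable across participants.

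Under the 7-draw list, only the 4 h and 8 h samples follow 2 h. When the observed peak falls at 2 h, a three-point terminal fit has to include the peak. This pulls λz down, t1/2 up, and the extrapolated part of AUC0-∞ up with it.

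The other two items decide what is reported. A 12-hour AUC cannot be observed when the last draw is at 8 h. A t1/2 taken literally from the abbreviation list could not be compared with the 108 minutes that the protocol cites.

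**Working it through.** **1. Counting the draws**

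| Source | Times (h) | Draws per participant | 24 participants |
|---|---|---|---|
| Footnote 8, 7.1.4, 7.2 | pre, 0.5, 1, 1.5, 2, 4, 8 | 7 | 24 × 7 = 168 |
| Table 2 PK row | pre, 0, 0.5, 1, 1.5, 2, 2.5, 3, 4, 8 | 10 | 24 × 10 = 240 |

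The difference of 240 − 168 = 72 draws is 24 × 3: Time 0, 150 and 180 minutes. The row has 11 cells under 11 column heads, and the vital-signs and dosing rows align in the same way, so a shifted table is unlikely. The pre-dose time also differs slightly: 7.1.4 fixes it at 30 minutes (±2) before dosing, while footnote 8 and 7.2 allow any time up to 30 minutes before.

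**2. AUC horizon**

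The last draw is at 8 h, or 8.25 h at the edge of its window. AUC0-12 therefore needs 12 − 8 = 4 h of extrapolation (12 − 8.25 = 3.75 h at best).

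**3. Effect on t1/2**

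The protocol states no PK figure to reproduce beyond the 108 minutes (1.8 h). The model below is illustrative.

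- From the protocol: half-life 1.8 h, so k = ln2/1.8 = 0.385 per hour.
- Assumed: one compartment, first-order absorption at rate ka, lag 0.25 h, ka from 3.0 down to 0.4 per hour. The protocol gives no Tmax.
- C(t) ∝ ka/(ka − k) × [exp(−k·t′) − exp(−ka·t′)], with t′ = t − 0.25.
- Tmax = 0.25 + ln(ka/k)/(ka − k).
- Fitted t1/2 = ln2 divided by minus the slope of ln C on the last three samples: 2, 4, 8 h (7-draw list) or 3, 4, 8 h (Table 2).

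Worked case, ka = 0.8 (Tmax 2.0 h): C at 2, 3, 4 and 8 h is 0.507, 0.455, 0.359 and 0.0936, with logs −0.679, −0.787, −1.024 and −2.369.

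- 2, 4, 8 h: slope = −5.403/18.667 = −0.2895, so t1/2 = 0.693/0.2895 = 2.39 h.
- 3, 4, 8 h: slope = −4.507/14 = −0.3219, so t1/2 = 0.693/0.3219 = 2.15 h.

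All cases (true value 1.8 h):

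| ka | Tmax (h) | Samples after observed peak, 7-draw / Table 2 | Fitted t1/2, 7-draw (h) | Fitted t1/2, Table 2 (h) |
|---|---|---|---|---|
| 3.0 | 1.0 | 4 / 6 | 1.8 | 1.8 |
| 1.2 | 1.6 | 3 / 5 | 2.0 | 1.9 |
| 0.8 | 2.0 | 2 / 4 | 2.4 | 2.15 |
| 0.5 | 2.5 | 2 / 3 | 3.5 | 2.9 |
| 0.4 | 2.8 | 2 / 2 | 4.5 | 3.6 |

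**4. The abbreviation list's t1/2**

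Solving C(t) = Cmax/2 after the peak over the same cases gives 2.2 to 4.3 h counted from the peak, or 3.2 to 7.1 h counted from dosing. The definition does not say which start applies. Neither reading returns 1.8 h.

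**5. Unsampled area**

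AUC0-t is proportional to ka/(ka − k) × [(1 − exp(−k·t′))/k − (1 − exp(−ka·t′))/ka]. At ka = 0.8 this is 2.349 to 8 h and 2.543 to 12 h, so (2.543 − 2.349)/2.543 = 7.6% of AUC0-12 would be extrapolated. A version without lag gives 4.5% to 13.0% for Tmax 1.0 to 2.5 h.

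**The case against.** The strongest reply is that the operative text is mostly sound. Cmax, Tmax and AUC0-t can be obtained from either schedule, and AUC0-∞ and t1/2 can be estimated for many profiles. AUC0-12 appears once, in the Synopsis, while every defining and analytic passage uses AUC0-t, so the subscript may be a slip or a misreading of a t. It should be checked in the source PDF. The t1/2 entry is one line in an abbreviation list, and naming non-compartmental analysis already implies a terminal slope. The objective is secondary and descriptive, with no test and no precision target. All of this stands, and it limits the severity.

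Three stronger readings are tempting but not supported:

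- *That the secondary PK endpoints as a group do not fit the sampling.* Only AUC0-12 is out of reach.
- *That the 7-draw list inflates t1/2 by up to 150%.* That is the slow-absorption edge, 4.5/1.8 = 2.5. At the same Tmax of 2.8 h Table 2 still gives 3.6/1.8 = 2.0, or +100%, because ka (0.40) is almost equal to k (0.385). For Tmax of 1.0 to 1.6 h the 7-draw list is off by only about 1% to 12%.
- *That the analyst will have to drop participants or fit through the peak.* Rules on point counts and extrapolation belong in the SAP, which is not shown and may contain them.

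What the reply does not answer is the conflict over the draws. An SAP can set rules for λz, but it cannot tell the site which schedule to follow on the day or restore samples that were not taken.

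**Conclusion.** The concern holds as three contradictions within the protocol: 7 against 10 PK draws; a 12-hour AUC against 8-hour sampling and AUC0-t elsewhere; and a t1/2 definition that does not match the stated method. The first matters most and rests on neither the model nor Tmax, only on Table 2 reading as extracted. The AUC item is subject to the check of the subscript.

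The numerical loss is confined to t1/2 and AUC0-∞ and is conditional on absorption. It is negligible if psilocin peaks at about 1 h. At a peak near 2 h the fitted half-life is overstated by about 33% (2.39/1.8) under the 7-draw list and about 20% (2.15/1.8) under Table 2. It is larger under both schedules for later peaks. These figures assume one compartment, a half-life of 1.8 h, a 0.25 h lag and noise-free concentrations. The document does not settle which schedule is intended.

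Severity: should be fixed, and before the first dose because the samples cannot be retaken.

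**What to change.** 1. **One PK draw list.** Reconcile footnote 8, 7.1.4 and 7.2 with Table 2, and use the same pre-dose window throughout. Keeping the 150- and 180-minute draws is preferable: they put samples in the 2 to 4 h gap and coincide with vital signs already scheduled every 30 minutes. They will need collection windows, since the text gives none for them. Remove the Time 0 mark, which duplicates pre-dose. That leaves 9 draws.
2. **Synopsis endpoint.** After checking the source PDF, change AUC0-12 to AUC0-t, as in Sections 4.4.2 and 12.4.
3. **Half-life.** Define t1/2 in the abbreviation list as ln2/λz, the terminal half-life from non-compartmental analysis. Leave the minimum number of terminal points and the extrapolation limit to the SAP.

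The cost is amendment wording plus two more small blood draws per participant than the section text lists (2 × 24 = 48 in all), both already marked in Table 2. The extra draws reduce the upward bias in t1/2 but do not remove it when absorption is slow.
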